1.1. STIs are an urgent public health concern for childbearing women

STIs are at a record high in the United States, and STI risk is an increasingly critical and costly health problem for American women, especially for pregnant women who can transmit the infections to their babies. STIs among women are associated with significant morbidity and mortality, including premature death. The American Congress of Obstetricians and Gynecologists (ACOG) and Centers for Disease Control and Prevention (CDC) reported that over the past decade, childbearing women have comprised one of the most rapidly expanding group infected by STIs, including HIV, in the U.S., and this epidemic is “accelerating in young women” Nearly 25% of pregnant women are infected with one of four STIs. Among those who had been treated for an STI in the past 6 months, 30% tested positive for a current STI during their pregnancy. Critical to this trend is the intersection of STIs and alcohol/drug use – both highly prevalent among women.

1.2. STIs and alcohol/drug use during pregnancy lead to significant biomedical risks to woman and fetus

A pregnant woman carries a risk of transmitting an STI to her infant during pregnancy, delivery, or breast-feeding, especially if untreated. STIs such as chlamydia and gonorrhea can be transmitted from the mother to her infant during the delivery, what the CDC laments as a “tragic systems failure.” Adverse effects of prenatal STIs can include miscarriage, ectopic pregnancy, stillbirth, low birth weight, neurological damage, and neonatal sepsis. Illicit drug use also has major health consequences for the pregnant women that can in turn negatively affect fetal development, rates of STIs, depression, intimate partner violence, as well as significant prenatal and neonatal complications (e.g., neurobehavioral and congenital abnormalities). Recent reviews suggest infants whose mothers used marijuana during pregnancy, compared to those who did not, were more likely to have lower birth rates and require neonatal intensive care. Prenatal alcohol exposure can lead to a wide range of adverse effects, known as Fetal Alcohol Spectrum Disorders (FASD) with an estimated 12,000 infants born with FAS each year, and up to three times as many have alcohol-related problems.

1.3. The intersection of STI and substance use disorders in the lives of pregnant women

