3.0. Specific Aims

Sexually transmitted infections (STIs) are at a record high in the United States, and STI risk is an increasingly critical and costly public health concern for American childbearing women. STIs and alcohol/drug use are interrelated and common morbidities that have significant direct and indirect relationships with health and functioning over the longer term for mother and fetus. Undetected and untreated STIs can lead to serious long-term consequences for childbearing women including infertility; for pregnant women, STIs can lead to a number of serious health risks including premature birth, low birth weight, increased need for neonatal care, and fetal death. Similarly, there has been a dramatic national increase in substance use during pregnancy, particularly opiate and marijuana use, leading to complications during pregnancy and poorer birth outcomes. Nearly one quarter of pregnant women are infected with an STI, and over 15% report some form of risky alcohol or drug use. Women who abuse substances are disproportionately more likely to engage in risky sexual behaviors that can result in STIs. Because of this intersection between substance use and STIs and because both are clearly associated with poor health outcomes, the ACOG and CDC strongly recommend targeting both risks during pregnancy.

Many challenges prevent the implementation of behavioral treatment programs in prenatal settings, and many women fail to engage in treatment even when it is readily available. These same women, however, may be willing to engage with brief, technology-delivered interventions that are tailored to their unique needs, and these approaches may be more applicable to be disseminated within overwhelmed prenatal care practices. Our team has successfully tested an innovative computer-delivered screening and brief intervention (SBI) program tailored for high-risk, non-treatment seeking pregnant women. Our preliminary results ($n = 50$) indicate that the Health Check-up for Expectant Moms (HCEM) is acceptable and feasible, and is associated with significant reduction in the key outcomes of alcohol or drug use ($OR = 0.15, p = 0.015$), with a trend toward significance in the reduction of unprotected sex ($OR = 0.17, p = 0.12$) during pregnancy.

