The objective of this proposed study is to build upon these promising R21 findings by testing whether HCEM, a computer-delivered SBI that simultaneously targets STI risk and alcohol/drug use during pregnancy, reduces antenatal and postpartum risk more than an attention, time, and information matched control condition among pregnant women seeking prenatal care. To meet this objective, we propose a two-group, randomized controlled trial in which a racially diverse sample of 250 pregnant women at risk for STIs and alcohol/drug use are recruited from high-volume prenatal care clinics or through telephone and online methods, and are assigned to either (a) a computer-delivered, single-session brief intervention plus two booster sessions; HCEM; or (b) a computer-delivered control condition. Computer and/or phone-delivered follow-up assessments will occur at 2 and 6 months, and extending to 6-weeks postpartum. Our biometric objective measures include STI incidence (e.g., chlamydia, gonorrhea) and birth outcomes. We propose the following Specific Aims:

Aim 1 (Primary outcomes): To test the hypothesis that HCEM, compared to an attention, time and information matched control condition, will reduce risk of STIs and alcohol/drug use among at-risk pregnant women during pregnancy at 2 and 6-months follow-up.

- (a) HCEM, as compared to control, will result in fewer unprotected sexual occasions;
- (b) HCEM, as compared to control, will result in lower alcohol use and illicit drug use, and fewer heavy episodic drinking days.

Aim 2 (Secondary outcomes): To test the hypothesis that HCEM will be associated with key secondary outcomes:

- (a) HCEM, as compared to control, will result in fewer STIs (re-infection and/or new infections) during pregnancy and at 6-weeks postpartum;
- (b) HCEM, as compared to control, will result in fewer unprotected sexual occasions and lower alcohol use and illicit drug use at 6-weeks postpartum;
- (c) HCEM, as compared to control, will result in better birth outcomes (e.g., low birth weight);
- (d) To collect and measure resource utilization and costs of HCEM to provide preliminary data to assess feasibility for future implementation and dissemination and to inform practice guidelines.

Aim 3 (Mediation): To explore direct and indirect effects in the above hypotheses:

- (a) To explore the effect of HCEM on the intermediate outcomes of pregnancy-specific knowledge and risk perceptions, autonomous motivation and self-efficacy during pregnancy;

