6.0. Retention: The research team has had retention rates (an average of 90%) in large treatment trials involving high-risk, low-income pregnant and postpartum populations. The current study will employ several approaches that we have found helpful in achieving these low attrition rates, including study staff's strong relationships with participants, efforts to value and appreciate the women's participation in the study, and frequent personal contact with the women for the duration of the study. Booster sessions will be web-based and accessible for participants to complete at home. RAs call women to remind them of their assessment appointments and maintain a list of two other people who will always know where the participant resides. Transport and childcare are provided as deemed necessary to complete assessments, particularly during the postpartum assessment. Compensation for participants' time helps facilitate retention.

A. Special circumstances affecting study retention

Because study eligibility includes being pregnant, and the HCEM is specifically tailored for pregnant women, in the event that an enrolled participant experiences a miscarriage, they will no longer be eligible for the study per the study research protocol. If study staff learns of miscarriage, study staff will call (or email if that is the preferred method of contact for the participant) the participant to follow up and offer Michigan Medicine resources for pregnancy loss, as well as notifying them of their new eligibility status.

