7.0. Data Analysis: Descriptive statistics will be calculated to summarize baseline characteristics for the full cohort and by intervention arm. Quality inspection will be carried out periodically to screen for missing-ness and data anomalies, and entry error. T-tests and chi-square-tests will be used to compare study arms with respect to demographic characteristics and baseline measures of unprotected sex and alcohol/drug use. Any identified confounders with $p \leq 0.10$ will be included in all subsequent analyses. Using the TLFB, we estimate the frequency of number of days in the 90-day period that the participant is engaged in a risky behavior. This will be carried out separately for each of the outcomes, namely, unprotected sex, illicit drug use and alcohol use, and heavy episodic drinking days (Hypothesis 1 and 2). The outcomes will be analyzed under a clustered count regression framework (Poisson or Negative Binomial) with frequency as outcome, and time (baseline, 2 months, 6 months), group (HCEM, control) and time-by-group interaction as the primary covariates. A generalized linear mixed models (GLIMMIX) approach will be adopted assigning a random subject intercept to account for the clustering within each participant. The regression model will be further controlled for potential confounders such as demographic characteristics, social desirability, and other variables that are identified to be significantly associated with outcome in the univariate analyses. We will adjust analyses for baseline pregnancy stage and assessment timing, as well as delivery status (delivered/not delivered) at follow up assessments in our data analysis, and pregnancy loss during course of study (e.g., miscarriage or stillbirth). Changes over time within each group will be estimated post-hoc by sliced effects derived from the regression model. In additional analysis, reduction in proportion of participants engaged in the risky behavior on ≥ 1 days within the 90-day period will be analyzed using a clustered logistic regression with a dichotomous outcome at the subject level indicating the status of the engagement, and with time (baseline, 2 months, 6 months), group (HCEM, control), time-by-group interaction as the primary factors. As before, a random subject intercept will account for the clustering and the model will be controlled for the same ensemble of covariates as in the case of the count regression models. Similar analyses will be conducted in the secondary aims for the outcomes that will be measured postpartum. To test hypothesis 3a and 3b, we will use structural equation modeling (SEM) approach. These include pregnancy-specific measures of autonomous motivation, self-efficacy, knowledge and risk perceptions (see Table 1). These measures are all continuous and will be measured at all three time points. All relevant direct and indirect effects will be evaluated. Significance of the indirect effect of the mediators will be tested using bootstrap method which appears to have good power in small samples. Birth outcome data will be available to the team by accessing patient medical records postpartum (Hypothesis 2c).

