10.0. Limitations and Countermeasures: Limitations of the current study include: potential issues related to disclosure of sensitive information, the use of self-report, assessment reactivity and effect on measured outcomes, the inclusion of only English-speaking participants, and generalizability of study results to other populations. To address these study limitations: 1) We will use technology to minimize socially desirable responses, particularly with stigmatizing behaviors, 2) we will directly assess and adjust for social desirability bias, 3) the baseline computerized assessment will occur prior to randomization to minimize bias; 4) loss to follow-up will be limited by computer-based assessment and home visits during postpartum assessment, and by our experience with long-term follow-up of high risk, vulnerable samples of women; 5) the information-matched control condition has been found acceptable and engaging in at least 4 behavioral studies that we know of including our own previous trials, and 6) based on data available at the clinic sites, there is only a small percent of women who are Spanish-speaking only. While participants will be recruited as close to first prenatal visit as possible, we will also include eligible high-risk women who are at later stages of pregnancy; we will adjust analyses for baseline pregnancy stage and assessment timing, as well as delivery status (delivered/not delivered) at follow up assessments in our data analysis, and pregnancy loss during course of study (e.g., miscarriage or stillbirth). We include monogamous pregnant women because STI risk is significantly elevated when substance abuse is present, regardless of partner status. Moreover, in our R21 study, 86% of the sample was monogamous, and yet intervention reduced condomless sex and substance abuse. We decided not to include genital herpes as an STI outcome as this is not in the clinical guidelines for STI screening set forth by the CDC. [name] will determine on a case-by-case basis for consideration of serological testing of genital herpes based on clinical presentation (e.g., active lesion) or partner history.

11.0. Project Timeline: We include a timeline detailing the proposed study activities (see Table 2, below).

11.1. Table 2. Planned Study Timeline		Year 1				Year 2				Year 3				Year 4				Year 5			
		1	2	3	4	1	2	3	4	1	2	3	4	1	2	3	4	1	2	3	4
HCEM Refinement, IRB, Hiring/Training Staff																					
Recruitment																					

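### Sections 7.0 and 10.0 adjust the main outcome models for delivery status and pregnancy loss, which arise after randomisation; baseline-only adjustment would be a cheap improvement, and any distortion is likely small

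*Combined protocol and SAP*

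**What the plan says.** Section 7.0 models days of risk behaviour in a 90-day recall window by Poisson or negative binomial mixed regression, with time, group, their interaction and a random intercept per woman. Among the covariates are pregnancy stage at baseline and timing of assessments, "as well as delivery status (delivered/not delivered) at follow up assessments in our data analysis, and pregnancy loss during course of study". The companion logistic models carry the same covariates.

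Section 10.0 repeats the rule, "we will adjust analyses for baseline pregnancy stage and assessment timing, as well as delivery status (delivered/not delivered) at follow up assessments", and gives its reason: "we will also include eligible high-risk women who are at later stages of pregnancy". No section names a main model without these terms or defines an analysis set.

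Other places bear on it:

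- Aim 1 (section 3.0) is that HCEM "will reduce risk of STIs and alcohol/drug use among at-risk pregnant women during pregnancy at 2 and 6-months follow-up". Section 5.5.2 sets the primary outcome at 8 weeks.
- Aim 2c is that "HCEM, as compared to control, will result in better birth outcomes (e.g., low birth weight". Section 5.5, item D, lists preterm birth and gestational age among the birth outcomes.
- Section 3.0 says that "STIs can lead to a number of serious health risks including premature birth, low birth weight, increased need for neonatal care, and fetal death". Section 1.2 says: "Adverse effects of prenatal STIs can include miscarriage, ectopic pregnancy, stillbirth, low birth weight".
- Section 6.0 A says that "in the event that an enrolled participant experiences a miscarriage, they will no longer be eligible for the study per the study research protocol".

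**The concern.** Randomisation protects a comparison adjusted for variables fixed at baseline. Delivery status at a follow-up visit and pregnancy loss are not fixed at baseline, and the protocol describes a route by which HCEM could alter both: fewer infections, hence fewer losses and premature births. If HCEM delays some deliveries and behaviour differs after delivery, part of its effect on behaviour runs through delivery, and the adjusted contrast removes that part. Unmeasured causes shared by delivery timing and behaviour would then add a second source of bias.

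What is at stake is the meaning of the 6-month result in Aim 1. A reader could not tell whether it is the effect of being assigned to HCEM or an effect with delivery status held fixed. Separately, the status of women who miscarry is worded differently in section 6.0 A than in sections 7.0 and 10.0, so two analysts could build different analysis sets.

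**Working it through.** The plan gives no figure for this point. The planning values used are those of section 7.4: means of 36 days at baseline, then 32 (control) and 29 (HCEM), with 100 women per arm.

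**1. Scale.** Planned log effect: ln(29/32) = -0.0984. Its Poisson standard error for one follow-up against baseline is √[(1/29 + 1/32 + 2/36)/100] = 0.0348.

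**2. Who can have delivered?** Section 4.0 puts the visits at 8 and 24 weeks, 16 weeks apart. Table 1 puts them at 19-28 and 36-39 weeks, read here as gestational age.

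- Second visit: 36 - 24 = 12 and 39 - 24 = 15, so both schedules fit only enrolment at 12-15 weeks.
- If Table 1 governs, nobody is past 40 weeks at the second visit.
- If the 24-week timing governs, women enrolled after 40 - 24 = 16 weeks are past 40 weeks. Section 10.0 sets no upper limit on stage at enrolment.
- First visit: 40 - 8 = 32, so a woman delivering at 40 weeks must have enrolled after 32 weeks to have delivered by then. At most 56 of the 90 recalled days can then follow delivery.

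**3. Simple illustration.** Let k be the daily rate after delivery divided by the rate before (assumed 0 to 1.25; section 5.0 says these behaviours increase postpartum). For a woman d days postpartum, r = 1 - (d/90)(1 - k). Let p0 be the share of controls delivered (assumed 5% to 20%) and p1 = p0 - 0.01 the HCEM share. The gap between total and adjusted log effects is ln[(1 - p1 + p1·r)/(1 - p0 + p0·r)], shown as a percentage of 0.0984. Plus means that adjustment overstates the total effect.

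| d | k | r | Gap |
|---|---|---|---|
| 14 | 0 | 0.844 | +1.6% |
| 14 | 1.25 | 1.039 | -0.4% |
| 28 | 0 | 0.689 | +3.2% to +3.4% |
| 28 | 1.25 | 1.078 | -0.8% |

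With p1 = p0, or k = 1, the gap is 0.

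**4. With enrolment and delivery dates.** All assumed: delivery at mean 39.2, SD 1.8 weeks; HCEM delays it by 0, 0.1 or 0.3 weeks; k of 0.05, 0.5 or 1.25; enrolment uniform over the range shown; visit at 24 weeks. Expected counts were fitted by Poisson regression with and without a delivered indicator.

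| Enrolment (weeks) | Controls delivered | Gap, stage-by-time term in both models | Gap, no such term |
|---|---|---|---|
| 8-16 | 14.7% | -0.6% to +2.2% | -0.6% to +2.3% |
| 8-24 | 54.9% | -0.3% to +1.3% | -1.6% to +7.7% |
| 8-34 | 72.3% | -6.6% to 0.0% | -1.7% to +13.0% |
| 29-34 | 100% (both arms) | 0 | 0 |

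The extremes all need k = 0.05 and a 0.3-week delay. On the log scale, 6.6% is 0.0065, or 0.19 standard errors; 13.0% is 0.0128, or 0.37. At the 8-week visit with k = 0.05, the gap is 0 for enrolment at 8-24 weeks and at most +1.4% for 8-34 weeks.

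**5. Terms entered once per woman.** In the log-link model, log mean = time + group + group×time + c·L + woman's intercept. Subtracting baseline from follow-up removes c·L, so an ever/never loss term cancels from the group-by-time contrast. Baseline stage without a time interaction cancels for the same reason, so the last column of step 4 is the relevant one if the plan means a main effect only.

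**6. Miscarriage, side by side.** Section 6.0 A ends eligibility. Sections 7.0 and 10.0 use miscarriage and stillbirth as a covariate, which presumes that these women are analysed. Section 6.0 A does not mention stillbirth. Section 7.3 imputes missing values generally and does not mention loss.

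**The case against.** The best defence is that Aim 1 concerns behaviour during pregnancy and Aim 2b covers postpartum behaviour separately, so adjusting for delivery moves towards the question asked. That stands in part, and it is why a delivery-adjusted analysis should be kept. But a delivered/not delivered indicator does not isolate pregnancy days, because a 90-day window can straddle delivery, and the plan does not say what the contrast means for women already delivered.

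It is also fair that exposure may be slight: section 5.1 recruits close to the first prenatal visit, and Table 1, if it governs, puts the second visit before 40 weeks. On miscarriage, sections 7.0 and 7.3 can be read as keeping these women and imputing their missing values. That is plausible but unstated.

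Three stronger readings are tempting and not supported:

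- **Late enrolment makes the distortion large, because whole recall windows fall after delivery.** Women enrolled from about 29 weeks reach the 24-week visit at 53 weeks or more. All have delivered in both arms, so HCEM cannot change their status and among them the gap is zero.
- **Adjusting for pregnancy loss biases the effect.** The wording reads naturally as one indicator per woman, which cancels from the count-model contrast. No section describes a loss term that varies by visit.
- **Assessment timing is a further fault.** The phrase may mean timing fixed at baseline, and nothing in the documents suggests that HCEM alters visit dates.

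**Conclusion.** The point holds as a minor one. The plan conditions its main models on events after randomisation that it expects HCEM may change, and names no model without them. The 6-month contrast is therefore the total effect of assignment only if HCEM leaves delivery timing unchanged.

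Size and direction cannot be derived from the documents, which give no distribution of gestational age at enrolment and no rates of delivery or loss by visit. Under the assumed inputs, and with stage modelled by time, the gap is mostly under about 2.5% of the planned log effect and at most about 6 to 7%. Without that term it can be larger, but only with wide enrolment, almost no sexual activity after delivery and a real shift in delivery dates; even then it is under 0.4 standard errors. The cancellation of the loss term is exact for the log-link count model and is not claimed for the logistic model.

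A reader might infer that the primary result is compromised. It is not: the 8-week outcome is barely exposed. The miscarriage limb is an inconsistency of wording plus missing detail, not evidence of bias.

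**What to change.** In sections 7.0 and 10.0:

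- Adjust the main models for baseline covariates only, including gestational age at enrolment and its interaction with time, since it largely determines who has delivered by each visit.
- State that all randomised women are analysed in their assigned arm, and that the main contrast is the effect of assignment whatever the delivery status.
- Move delivery status and pregnancy loss to labelled sensitivity analyses. To serve Aim 1, include either a delivery-adjusted analysis or one restricted to timeline follow-back (TLFB) days before delivery. The latter drops women with no such days in the window, since a log-days offset is undefined at zero. The plan should say that this is selection on an event after randomisation.
- Report pregnancy losses by arm.

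Reconcile sections 6.0 A, 7.0 and 10.0 on women who miscarry, including whether their data are kept and whether the section 7.3 imputation covers their later visits. This review does not choose the follow-up rule.

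The cost is some wording and one table row. No visit or measurement is added, because the TLFB is a calendar and gestational age at birth is already collected; the sample size does not change. The downside is that the main 6-month estimate mixes days before and after delivery, which the sensitivity analysis would show.
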